3.3.3. Study procedures

[figure not shown]
In the pre-implementation phase

(month -6 to month 6), study and comparison clinics (selected as already having high-quality TB records) will continue to maintain standard TB registers. These registers include all individuals who have sputum sent for TB diagnosis with sputum smear and/or Xpert ("presumptive register") and all individuals who are started on TB treatment ("treatment register"). We will abstract key data from these registers, including age, sex, prior TB treatment, HIV status, diagnostic result, and treatment outcome. During month 1 of the study, we will initiate a retrospective abstraction of all registers from month -6. We will also begin prospective abstraction of registers by having routine clinic staff take photos of registers and securely transfer them to our study team, who will upload these into a REDCap database. Staff from the XPEL-TB trial⁴⁴ have experience in these procedures (including the development of a pre-existing database for this purpose), so we will be able to initiate this abstraction rapidly and seamlessly.

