In the **post-implementation phase** (months 7-18), we will encourage all eight clinics (study and comparison clinics) to continue high-quality record-keeping as during the pre-implementation phase. The four study clinics

Figure 2. Study Overview

will be asked to maintain records of the PredicTB score sheets for all patients on whom the score was calculated. We will also perform quarterly site visits that will include the following components:

- Review of the quality of record-keeping and transmittal of records to study staff [all clinics];
- Collection of cost data, including budgetary review and time-and-motion studies [study clinics];
- Assessment of PredicTB reach (proportion of patients receiving same-day empiric treatment initiation), adoption (proportion of clinicians adopting PredicTB), and implementation (proportion of patients in whom PredicTB was used as indicated) [study clinics]; and
- Performance feedback to clinic staff regarding TB diagnosis and treatment outcomes [all clinics].

During this phase, we will also perform mycobacterial culture (using both solid [Lowenstein-Jensen] and liquid [Mycobacteria Growth Indicator Tube, MGIT; BD Diagnostics, Sparks, MD, USA] media) on all sputum specimens from all eight clinics that are Xpert-negative but correspond to adult patients who were empirically initiated for TB. *These culture results will not be used for any of our primary effectiveness analyses* but instead will be used to estimate the sensitivity and specificity of empiric treatment decisions, both with and without the PredicTB score. Specimens will be sent from the central laboratories in which Xpert is performed, rather than from study clinics themselves, so as to minimize interference with study clinic procedures. Nevertheless, culture results will be transmitted back to clinicians to assist with management.

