3.3.4. Analysis Plan

Table 1. Overview of Analysis Plan

Specific Aim	Analytic Goal	Primary Outcomes (1° outcome underlined)	Secondary Analyses	Analytic Strategy
Aim 1	Evaluate PredicTB Effectiveness	Differences in proportions (pre-post): Treatment initiation (1a) Mortality (1b) Loss to follow-up (1b) Difference in differences (study – comparison) (1c)	Adjustment for age, sex, HIV status, treatment history Regression discontinuity	Mixed-effects log-binomial models (clinic as random effect) Parametric regression discontinuity analysis Difference-in-difference ("product term") model
Aim 2	Evaluate PredicTB Implementation	Reach (2a): % same-day empiric treatment Adoption (2b): % providers using PredicTB Implementation (2c): % of encounters using PredicTB as indicated Maintenance (2d): chg in effectiveness over time	Validation with patient surveys Sensitivity/specificity of empiric tx decisions Association with patient level characteristics	Binomial distribution & confidence intervals w/ clustering by clinic Mixed-effects log-binomial models
Aim 3	Estimate PredicTB Impact & Cost-Effectiveness	Projected reduction in 5-year TB mortality (3a) Incremental cost per DALY averted (3b)	Probabilistic sensitivity analyses Uncertainty analyses Unit cost estimation	Markov state-transition model Cost-effectiveness analysis

Aim 1. Evaluate the effectiveness of the PredicTB clinical risk score on clinical outcomes. Our primary analysis will estimate the absolute difference in the proportion of patients with microbiologically confirmed TB (Xpert or smear; study-driven culture results will be excluded) who are initiated on anti-TB treatment within 7 days of submitting an initial sputum specimen for TB diagnosis, comparing the post-initiation period to the pre-initiation period (dark minus light blue in Figure 2). We will estimate this quantity using a multilevel log-binomial

model, with random-effect terms corresponding to each of the four study clinics. We will perform similar analyses for the proportion of patients with TB who complete treatment and die from any cause (Aim 1b).

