This analysis is subject to bias resulting from both secular trends and non-intervention-related effects. We will therefore also perform a difference-in-differences analysis, comparing pre-post effects in the study clinics to those observed in the comparison (non-PredicTB) clinics (Aim 1c). We have not made this our primary analysis because the comparison clinics are smaller (thereby reducing power) and not randomly allocated – for example, staff in these clinics may be less motivated to change behavior. We will also perform a parametric regression discontinuity analysis to estimate the causal effect of implementing the PredicTB risk score (with the discontinuity occurring at the time of implementation). This analysis, however, has less statistical power, and the shape of the effectiveness curve over time in the post-implementation period may reflect important effects (i.e., we are interested not only in the immediate effect of the intervention but also its maintenance over time).

Sample size considerations. Based on patient volumes in 2019, we anticipate a sample size of 1100 patients with confirmed TB: 550 pre-intervention and 550 post-intervention. Using data from our STOMP-TB study,¹³ we expect that 55% of patients will initiate treatment within 7 days in the pre-intervention period. Assuming a design effect of 1.67 due to clustering by clinic, we will have 80% power to detect a difference if treatment initiation increases to 66% in the post-intervention phase and 97% power if treatment initiation increases to 70% (Figure 3).

[figure not shown]

Figure 3. Study power

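### Culture covers only months 7-18 and only empirically treated Xpert-negatives, so accuracy with and without PredicTB has no baseline and culture-referenced sensitivity and specificity are not identified

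*Combined protocol and SAP*

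**What the plan says.** Section 3.3.3 (post-implementation phase, months 7-18) introduces the reference standard: "During this phase, we will also perform mycobacterial culture". It is to be done "on all sputum specimens from all eight clinics that are Xpert-negative but correspond to adult patients who were empirically initiated for TB". The results stay out of the primary effectiveness analyses; instead they "will be used to estimate the sensitivity and specificity of empiric treatment decisions, both with and without the PredicTB score". Neither condition is defined.

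In section 3.3.4, Table 1 lists the item as "Sensitivity/specificity of empiric tx decisions" among the secondary analyses of Aim 2, with no period, comparator or contrast. The pre-post and difference-in-differences analyses in that section belong to Aim 1.

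For months -6 to 6, section 3.3.3 plans register abstraction and no culture. Of the registers it says: "These registers include all individuals who have sputum sent for TB diagnosis with sputum smear and/or Xpert". A second register lists everyone started on treatment. On content: "We will abstract key data from these registers, including age, sex, prior TB treatment, HIV status, diagnostic result, and treatment outcome".

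Section 3.3.4 describes the comparison clinics as smaller and "not randomly allocated – for example, staff in these clinics may be less motivated to change behavior". Section 3.3.1 adds that two selection criteria, case volume and a willing in-charge, were relaxed for them.

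**The concern.** A tool that prompts empiric treatment can be expected to make it more frequent. For a later trial, the useful question is whether decisions also become better. Accuracy estimates under two labelled conditions invite that reading, and two features of the plan prevent it.

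First, nothing culture-based exists before implementation. If *without* means the comparison clinics, the contrast mixes the score with standing differences in how freely each clinic treats empirically. If it means study-clinic patients for whom no score sheet was completed, the clinician decided who was scored. Clinics that always treated more freely would look more sensitive and less specific with no effect of the score, and the reverse could hide a real effect.

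Second, a patient is cultured only because treatment was started. Xpert-negative, culture-positive patients who were left untreated are the missed cases that a sensitivity estimate must count, and they are never observed.

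**Working it through.** **1. The plan's own figure.** The plan gives no sample size or precision for this analysis. Its only power figure is for the primary outcome: 550 per period, 55% against 66% or 70%, design effect 1.67. With effective n = 550/1.67 = 329 per period and two-sided alpha 0.05 (assumed; none is stated), a two-proportion test with continuity correction gives 80.3% and 97.5%, against 80% and 97% stated (82.5% and 97.9% uncorrected). That figure is sound but does not bear on this point.

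**2. What each period can supply.**

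| | Months -6 to 6 | Months 7-18 |
|---|---|---|
| Smear and/or Xpert result, all tested | yes | yes |
| Treatment starts | yes | yes |
| Culture, Xpert-negative and treated empirically | no | yes |
| Culture, Xpert-negative and untreated | no | no |

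The third row shows the missing baseline. The fourth shows that repeating the same culture rule at baseline would not repair the estimate.

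**3. Identification.** All counts here are assumed, since the documents give none: 1,000 tested; P = 100 Xpert-positive, of whom a = 40 were treated empirically; 900 Xpert-negative, of whom T = 90 were treated empirically and c = 9 of those are culture-positive; U = 900 - 90 = 810 untreated and uncultured. Let q be the unknown proportion of the 810 who are culture-positive.

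- Sensitivity = (a + c) / (P + c + qU) = 49 / (109 + 810q)
- Specificity = (1 - q)U / [(1 - q)U + (T - c)] = 810(1 - q) / [810(1 - q) + 81]

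| q | Sensitivity | Specificity |
|---|---|---|
| 0% | 49/109 = 45.0% | 810/891 = 90.9% |
| 2% | 49/125.2 = 39.1% | 793.8/874.8 = 90.7% |
| 5% | 49/149.5 = 32.8% | 769.5/850.5 = 90.5% |
| 10% | 49/190 = 25.8% | 729/810 = 90.0% |

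The planned data carry no information on q. Counting the uncultured as free of TB gives the top row. Leaving them out instead removes every untreated Xpert-negative patient, so specificity becomes 0/81. Against Xpert alone, the same patients give 40/100 = 40% and 810/900 = 90%, with nothing unobserved.

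**4. Chance differences between clinic groups.** For four clinics against four, SE = SD × √(1/4 + 1/4), and the 95% half-width is 2.447 × SE (t, 6 df). The SD of the clinics' empiric-treatment rates is assumed.

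| SD (points) | SE | Half-width |
|---|---|---|
| 5 | 3.5 | 8.7 |
| 10 | 7.1 | 17.3 |
| 15 | 10.6 | 26.0 |

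These are differences in the treatment rate with no effect of the score and before any selection. They show the scale of standing clinic differences. They are not errors in sensitivity or specificity.

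**5. Does a before-after contrast help?** Stable clinic differences cancel. On the same basis, with correlation ρ between a clinic's two period rates, the variance of a clinic's change is 2·SD²(1 - ρ), so the SE of the difference-in-differences is SD × √(1 - ρ). With SD 10 this is 8.4 at ρ = 0.3, 7.1 at ρ = 0.5 and 4.5 at ρ = 0.8. It beats the cross-sectional SE of 7.1 only if ρ exceeds 0.5, which the documents do not give. The gain that can be relied on is removal of stable confounding; better precision is conditional.

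**The case against.** The best defence is that the plan promises only to estimate accuracy under each condition. It never says that the difference will be presented as an effect of the score, and it keeps culture out of the primary effectiveness analyses. That stands, and it limits the severity. It does not rescue the estimates: even as pure description, culture-referenced sensitivity needs culture results from untreated patients.

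A second objection is that registers cannot replace culture. A reader might infer that they allow the same measure before implementation. They do not: they hold smear and/or Xpert results, so they support only a different, routinely referenced measure. Section 3.3.1 says smear is still the main assay in Uganda, so an Xpert-only reference would drop smear-only patients. The month-7 training in standard diagnosis in all eight clinics could also shift the test mix. These points stand and shape the fix.

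Third, same-day starts among test-positive patients come close to Aim 1a with a shorter window, and Aim 1 already has both contrasts. That is fair for this half. The test-negative half is new: no Aim 1 analysis shows whether starts among test-negative patients rise after implementation.

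**Conclusion.** The concern holds in a limited form. Culture-based accuracy has no baseline, its two conditions are undefined, any available contrast is cross-sectional and non-randomised, and selective culture leaves sensitivity and specificity unidentified. In the assumed example the unknown moves sensitivity by about 19 points (45.0% to 25.8%) and specificity by about 1 point. Those sizes depend entirely on the assumed counts; the lack of identification does not.

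Three stronger inferences are not supported. A reader might conclude that the plan commits to comparing study with comparison clinics, but the text leaves *without* open. A reader might take half-widths of 9, 17 or 26 points as the error in the accuracy estimates, but they concern the empiric-treatment rate under assumed SDs. And a reader might think that the primary result is affected, which the exclusion of culture from that analysis rules out. This is a secondary Aim 2 analysis in a preliminary study, and the change is worth making because it is cheap.

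**What to change.** 1. Define *with* and *without* PredicTB as the study clinics after versus before implementation, with the comparison clinics as control.
2. From the registers, for months -6 to 6 and 7-18 in all eight clinics, compute the proportion with a same-day treatment start among Xpert/smear-positive adults and among Xpert/smear-negative adults. Count starts prompted by a same-day positive smear separately from empiric starts. Report the within-clinic change and its difference-in-differences, and the smear/Xpert mix by period.
3. Report culture only as the proportion positive among empirically treated Xpert-negatives, as a description of the post-implementation period and not as an effect of the score.

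The cost is SAP wording and further analysis of registers already being abstracted, including matching test-negative patients to the treatment register. It assumes that sputum and treatment-start dates are captured; the listed fields do not name them, but the 7-day primary outcome needs them. No new specimens are required.

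The limits should be stated in the SAP: the routine reference misses Xpert-negative, culture-positive TB; a change in test mix could alter it between periods; and the difference-in-differences removes stable clinic differences without necessarily being more precise.

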3.2. Preliminary Studies and Experience

3.2.1. The PredicTB Risk Score

Our team has developed a simple clinical risk score (“PredicTB”) for predicting active pulmonary TB in settings where same-day microbiological testing is not available (Figure 1). This score was developed using data from 1,387 adult patients who presented with classical TB symptoms (cough, fever, weight loss, night sweats) at 28 primary health clinics in rural Limpopo district, South Africa, and for whom a sputum Xpert test for TB was ordered.¹² We then externally validated this score using data from 387 patients who presented with TB symptoms and were

[figure not shown]

Figure 1. A simple clinical risk score (PredicTB) for initiation of empiric TB treatment when same-day testing is not available

tested using Xpert in four primary health clinics in Kampala, Uganda. This clinical risk score is designed for ease of use, being scored on a scale from 1-10 and using only readily accessible demographic and clinical data (sex, age, self-reported HIV status, self-reported diabetes status, number of symptoms, and duration of symptoms >14 vs ≤14 days; see Figure 1). The c-statistic for this easy-to-use risk score in the validation population was 0.75, consistent with other scores using more detailed clinical data,^{34–38} and decision curve analysis indicated that the net utility of using this score (at a cutoff of ≥5/10) would be significantly higher than no empiric treatment. As an example, a person with a PredicTB score of 7/10 in a population where 10% of all diagnostic Xpert tests are positive (i.e., pre-test probability of 0.1) would have a calculated 43% chance of having TB – a post-test probability that likely is sufficiently high to merit same-day empiric treatment. *De novo* development of a corresponding score in the Ugandan population resulted in very similar attributes being selected (diabetes was dropped and antiretroviral status plus observed cough were added), and very similar performance (validation c-statistic of 0.78).¹² This easy-to-use risk score is therefore sufficiently accurate to improve clinical decision-making in the most-resource-constrained settings; the proposed study will evaluate whether real-world implementation of this score can improve patient outcomes as well.

3.2.2. Impact of same-day diagnostic testing for pulmonary TB on patient outcomes in Uganda

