3.3 Research Design and Methods

3.3.1. Study setting and design

We will conduct this study in four primary health clinics in peri-urban Uganda (with four additional clinics serving as a comparison). Uganda is one of 30 high TB burden countries recognized by World Health Organization (WHO), with an estimated 2018 TB incidence of 200 per 100,000; 41% of those cases were co-infected with HIV.¹ Like many countries in East Africa, Uganda is among the world's poorest countries with an estimated per-capita gross domestic product (GDP) of \$777 2019;⁶⁰ the drivers of its TB epidemic are multifaceted,⁶¹ and there is relatively little drug resistance. Most TB in Uganda is diagnosed in public sector health facilities, and despite national guidelines promoting the use of Xpert, sputum smear microscopy remains the primary diagnostic assay used.⁵⁴ Diagnostic and treatment delays are common,⁶² resulting in a large number of untreated prevalent cases; the 2014-15 Ugandan National TB Prevalence Survey⁶³ estimated the prevalence of bacteriologically confirmed TB at 401 per 100,000 adults. These conditions are typical of sub-Saharan Africa (outside of South Africa); thus, findings from our study are likely to be broadly relevant.

We have selected four study clinics based on the following criteria: (a) within 150km of the capital city, Kampala; (b) no access to same-day Xpert testing (a criterion that effectively excludes clinics in Kampala proper); (c) high-quality TB record-keeping; (d) at least 100 bacteriologically confirmed TB cases diagnosed in 2019 (which effectively excludes private-sector clinics); and (e) clinic in-charge willing to have clinic staff trained in use of the PredicTB tool. We have also selected four comparison clinics that are similar in location and patient population to the four primary study clinics, but for which the latter two criteria were relaxed.

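### Because only empirically treated Xpert-negative patients are cultured, a culture-inclusive sensitivity of empiric treatment decisions is not identified; among Xpert-tested patients it is an upper bound

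*Combined protocol and SAP*

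**What the plan says.** Section 3.3.3 (post-implementation phase) provides for solid and liquid culture, in all eight clinics, of sputum specimens "that are Xpert-negative but correspond to adult patients who were empirically initiated for TB". The results are to be "used to estimate the sensitivity and specificity of empiric treatment decisions, both with and without the PredicTB score". On logistics, "Specimens will be sent from the central laboratories in which Xpert is performed, rather than from study clinics themselves". The same paragraph sets a limit: "These culture results will not be used for any of our primary effectiveness analyses".

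Table 1 in section 3.3.4 carries the analysis as "Sensitivity/specificity of empiric tx decisions", in the secondary column for Aim 2. Neither place names a reference standard, says whether the decision assessed is a same-day start or any empiric start, or mentions bounds or a correction for partial verification.

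Two other statements bear on who can be cultured. Section 3.3.1 says of Uganda generally that "sputum smear microscopy remains the primary diagnostic assay used". Section 3.3.3 says of the presumptive registers: "These registers include all individuals who have sputum sent for TB diagnosis with sputum smear and/or Xpert".

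**The concern.** Sensitivity needs the false negatives: patients with TB whom the clinician did not treat empirically. For Xpert-positive TB the registers supply them. For Xpert-negative TB only culture could, and culture depends on the patient having been treated. If the decision assessed is any empiric start, culture can add true positives but no false negatives, so the ratio is pushed up.

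Nothing in sections 3.3.3 to 3.3.5 closes the gap. The register abstraction brings no culture, the 100 end-phase surveys do not mention it, and the Aim 2 validation at site visits concerns use of the score, not disease status.

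At stake is the planned measure of how accurately clinicians treat empirically, with and without the score, in a study meant to inform whether a larger trial is worth running. Specificity has the same missing cell, and smear-only patients create a separate gap for both measures.

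**Working it through.** The plan states no expected value or precision for this analysis, so there is no figure to reproduce. The check is a bounds argument, then a grid of assumed inputs. Xpert-positive and culture-positive are both taken as true TB, and clustering is ignored.

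**Bound, Xpert-tested patients, any empiric start.** Let a = Xpert-positive treated empirically, b = Xpert-positive not so treated, c = Xpert-negative treated and culture-positive, d = Xpert-negative treated and culture-negative, U = Xpert-negative untreated, and u = unknown TB cases within U.

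- True sensitivity = (a+c)/(a+b+c+u).
- Observable = (a+c)/(a+b+c), which is the value at u = 0 and so the maximum.
- True specificity = (U-u)/(U-u+d), also largest at u = 0.

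**Same-day decision.** Split c into c1 (same-day start) and c2 (later start), and let a1 be the same-day part of a. Observable = (a1+c1)/(a+b+c1+c2); truth adds u to the denominator. The c2 patients are verified false negatives, so the gap is narrower, but u remains.

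**Size among Xpert-tested patients.** Assumed: Xpert sensitivity s = 0.7, 0.8, 0.9; fraction p of Xpert-positive TB treated empirically = 0.2, 0.5, 0.6; fraction e of Xpert-negative TB so treated = 0.2, 0.4, 0.6. Per 100 Xpert-positive, Xpert-negative TB is x = 100(1-s)/s. True = (100p+xe)/(100+x); reported = (100p+xe)/(100+xe).

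- Largest error: p=0.6, s=0.7, e=0.2 gives x=42.86; true 68.57/142.86 = 48.0%; reported 68.57/108.57 = 63.2%; error +15.2.
- Smallest error: p=0.2, s=0.9, e=0.6 gives x=11.11; true 26.67/111.11 = 24.0%; reported 26.67/106.67 = 25.0%; error +1.0.

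The last column is the difference reported when only e rises, from 0.2 to 0.6. The true difference is (1-s) x 0.4 = 4.0 to 12.0 points at every p.

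| p | Overstatement (points) | Reported difference (points) |
|---|---|---|
| 0.2 | 1.0 to 6.3 | 3.3 to 10.0 |
| 0.5 | 2.1 to 12.9 | 2.0 to 6.3 |
| 0.6 | 2.5 to 15.2 | 1.6 to 5.0 |

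**Contrast when unverified TB differs between groups.** Write u = qU. Illustrative groups: without the score a+b=100, a=50, c=10, U=760; with the score a+b=100, a=50, c=20, U=740.

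- q = 0 in both: 60/110 = 54.5% and 70/120 = 58.3%, difference 3.8. Any equal q from 0 to 5% gives 3.8 to 4.0.
- q = 3% without, 1% with: 60/132.8 = 45.2% and 70/127.4 = 54.9%, difference +9.8 from unrounded values.
- Reversed: 60/117.6 = 51.0% and 70/142.2 = 49.2%, difference -1.8.

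**Smear-only patients pooled in.** Assume 50% smear-only and smear sensitivity 50%, and take 100 TB patients, 50 in each testing group.

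- s=0.9, p=0.2, e=0.6: 45+25 = 70 test-positive, 5+25 = 30 test-negative. True = (14+18)/100 = 32.0%. Only 3 of the 18 treated test-negatives are cultured, so reported = (14+3)/(70+3) = 23.3%; error -8.7.
- s=0.7, p=0.5, e=0.2: 60 test-positive, 40 test-negative. True = (30+8)/100 = 38.0%; reported = (30+3)/(60+3) = 52.4%; error +14.4.

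**Specificity.** Section 3.2.1 uses, as an example, "a population where 10% of all diagnostic Xpert tests are positive". Take 1,000 Xpert-tested at that rate, and assume 15% of the 900 negatives are treated and 10% of those are culture-positive: U=765, d=121.5. Specificity is 86.3% at u=0, 86.2% at q=1% and 85.0% at q=10%, so it moves little. With half of patients smear-only (same smear sensitivity, true specificity 85% or 97%, s=0.7 or 0.9, e=0.2 or 0.6), the error runs from -2.2 to +0.1 points, because treated smear-negative TB is counted as false positive.

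**The case against.** **The reference may be Xpert or smear alone.** Sensitivity is then identified, since those results exist for treated and untreated patients. But the cultures contribute nothing to it, contrary to the purpose given for them. It is also a different quantity. At p=0.2, s=0.7, e=0.6 it gives 20% where all-TB sensitivity is 32.0%, and it shows no change when the score alters treatment only of Xpert-negative TB. A reader might take it as the corrected figure; it is not.

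**The error may cancel between groups.** It roughly does in the illustration if q is equal. The plan gives no ground for equality: the score is meant to change who is treated, and section 3.3.4 says the comparison clinics are smaller and not randomly allocated.

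**Culture could verify some false negatives.** This stands if the same-day decision is meant. The culture rule does not say same-day, while section 3.3.3 defines reach by same-day starts. A reader might infer that culture can never reveal a false negative; the text does not support that without knowing the decision.

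**The upper bound may not apply to everyone.** This also stands. A reader might infer that the figure is too high for all patients in every group. With smear-only patients included it can be too low, so the bound holds only among the Xpert-tested. The documents do not give the smear-only share in these clinics.

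**It is a secondary analysis resting on assumed sizes.** Both are true. No decision rule depends on the estimate.

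**Conclusion.** The point holds for Xpert-tested patients. Under the stated culture rule, a culture-inclusive sensitivity of any empiric start is an upper bound, equal to the truth only if no untreated Xpert-negative patient has TB. A same-day definition narrows the gap without closing it. Under the assumed ranges the overstatement is about 1 to 15 points. A true gain of 4.0 to 12.0 points confined to Xpert-negative TB is under-reported throughout, and the contrast can change sign if unverified prevalence differs between groups. With smear-only patients pooled in, the direction is unknown.

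The non-identification follows from the design; the sizes rest on assumptions, since the documents give none of the needed rates for these clinics. A reader might divide the 550 confirmed patients per period by the 10% positivity to get a count of missed cases. The documents do not support that: the 550 are confirmed by Xpert or smear, the 10% is an illustrative Xpert-only rate, and the comparison clinics, which are also cultured, are left out. Nor is the primary effectiveness outcome affected, because culture is kept out of it.

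**What to change.** Amend the culture paragraph of section 3.3.3 and the Aim 2 row of Table 1:

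1. Use the cultures to report the proportion culture-positive among Xpert-negative, empirically treated patients, with and without PredicTB. The planned data do identify this.
2. Restrict any culture-inclusive sensitivity or specificity to Xpert-tested patients, and state whether the decision is a same-day start or any empiric start. Label the sensitivity an upper bound, and give bounds over an assumed TB prevalence q in untreated Xpert-negative patients, varied separately with and without PredicTB.
3. If sensitivity against Xpert or smear alone is reported, label it as a different estimand that says nothing about Xpert-negative TB.

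This needs wording and analysis only, with no extra cultures. The cost is giving up a culture-inclusive point estimate of sensitivity, which the planned data cannot support.
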